7. STUDY DESIGN

7.1. Overall Design

Our overall goal is to understand the role somatosensation plays in modulating analgesia and neuroimaging markers related to altered neural processing of pain in FM (Table 1; Figure 2). Eighty (80) FM women patients will be evaluated with MRI at baseline and after acupuncture treatment (electro-acupuncture, EA; mock laser acupuncture, ML; n=40 per group). Treatments will be delivered at 2x/week for 4 weeks, for a total of 8 treatments. An additional 40 healthy age-matched adult women will serve as a control for neuroimaging markers collected from baseline FM patients, and will allow us to assess central pain pathology in our population (Aim 1). The HCs will not be treated with acupuncture since the goal of this investigation is to investigate potential mechanisms for acupuncture in chronic pain patients. In addition to our neuroimaging outcomes, we will also assess clinical and experimental pain outcomes during the study period from all subjects. These data in combination with other outcomes will be used to perform secondary analyses.

Table 1 – Neuroimaging Outcomes

Outcome	fMRI Protocol	Rationale
Clinical Pain	- resting fcMRI and ¹ H-MRS	Neuroimaging markers for clinical pain directly reflect our primary clinical outcome. Markers are needed for localized brain neurochemistry and associated network connectivity and their relation to clinical pain.
Experimental Pain	- fMRI with pressure pain and conditioned pain modulation.	Protocols for brain response to experimental pain are more mature than for clinical pain (facilitating comparison to prior research) and allow the assessment of hyperalgesia and allodynia.

7.2. Schema

[figure not shown]

Figure 2– Experiment overview. EA = electro-acupuncture, ML = mock laser “sham” acupuncture (without somatosensation).

8. PATIENT SELECTION AND ENROLLMENT

8.1. Patient Eligibility

8.1.1. Inclusion Criteria

Inclusion Criteria for Fibromyalgia Participants

- Must have self-reported FM symptoms for at least one year and also meet the newly proposed Wolfe et al 2011 criteria for FM. Continued presence of pain more than 50% of days.
- Pain greater than or equal to 4 on a 10cm Visual Analog Scale (VAS) for pain; 7-day recall; [Note: The VAS is widely used in clinical pain research and as such we chose to use it for inclusion criteria and for clinical pain assessment below. Within our group numerical ratings scales 0-100 are more commonly used in quantitative sensory assessment, and as such we chose to use NRS scales for evoked pain assessments below.]
- Willing to limit the introduction of any new medications or treatment modalities for control of FM symptoms during the study.
- Able to travel to the study site to receive acupuncture treatments up to two times weekly.
- Over 18 and under 65 years of age.
- Right-handed.
- Female.
- Capable of giving written informed consent.

Inclusion Criteria for Healthy Control Participants

- Over 18 and under 65 years of age.
- Female.
- Right-handed.
- Pain equals 0 on a 10cm Visual Analog Scale (VAS) for pain; 7-day recall
- Willing to complete all study procedures.
- Capable of giving written informed consent.

8.1.2. Exclusion Criteria

Exclusion Criteria for Fibromyalgia Participants:

- Acupuncture within last 6-months.
- Presence of a known coagulation abnormality, thrombocytopenia, or bleeding diathesis that may preclude the safe use of acupuncture.
- Presence of a concurrent autoimmune or inflammatory disease such as rheumatoid arthritis, systemic lupus erythematosus, inflammatory bowel disease, etc. that causes pain or any other chronic pain condition with pain greater than FM pain.
- History of head injury with substantial loss of consciousness
- Peripheral neuropathy of known cause that interferes with activities of daily living.
- Routine daily use of narcotic analgesics, marijuana, or history of substance abuse.
- Stimulant medications, such as those used to treat ADD/ADHD (e.g., amphetamine/ dextroamphetamine [Adderall®], methylphenidate, dextroamphetamine), or the fatigue associated with sleep apnea or shift work (e.g., modafinil), are excluded.
- Concurrent participation in other therapeutic trials.
- Pregnant or nursing.
- Severe psychiatric illnesses (current schizophrenia, major depression with suicidal ideation).

- Active substance abuse disorder in the past 24 months as determined by subject self-report
- Use of PRN over the counter (OTC) pain medications (NSAIDs, etc.) on day of MRI scan.
- Use of PRN narcotic pain medication 48 hours prior to MRI scan.
- Contraindications to fcMRI, fMRI, or ¹H-MRS methods. These may include but are not limited to: surgical clips, surgical staples, metal implants, and certain metallic dental material. [Note: a more formal description of contraindications for MRI is present in our DSM Plan].
- Any impairment, activity or situation that in the judgment of the Study Coordinator or Principal Investigator that would prevent satisfactory completion of the study protocol. This includes unreliable, or inconsistent pain scores as deemed by the principal investigator.
- Current, habitual, or previous use within the last 12 months of artificial nails, nail enhancements, or nail extensions that cover any portion of either thumbnail. Exceptions, including brief and/or occasional use, may be permissible at the discretion of the principal investigator.
- Contraindications to the Electrostimulator device: Participants with electrical implants (i.e. pacemakers, defibrillators), cardiac rhythmic disorders, seizure disorders, any skin disorders in the vicinity of the electrode or any malignant diseases in the region of application.
- History vascular surgery in lower limbs or current lower limb vascular dysfunction.
- Subjects with Worker's Compensation, Workman's Compensation, civil litigation or disability claims pertinent to the subject's fibromyalgia; current involvement in out-of-court settlements for claims pertinent to the subject's fibromyalgia; or currently receiving monetary compensation as a result of any of the above.

Exclusion Criteria for Healthy Control Participants:

- Have a diagnosis of FM or meet the newly proposed Wolfe et al 2011 criteria for FM.”
- Presence of a concurrent autoimmune or inflammatory disease such as rheumatoid arthritis, systemic lupus erythematosus, inflammatory bowel disease, etc. that causes pain.
- History of head injury with substantial loss of consciousness
- Peripheral neuropathy of known cause that interferes with activities of daily living
- Routine daily use of narcotic analgesics, marijuana or history of substance abuse.
- Stimulant medications, such as those used to treat ADD/ADHD (e.g., amphetamine/ dextroamphetamine [Adderall®], methylphenidate, dextroamphetamine), or the fatigue associated with sleep apnea or shift work (e.g., modafinil), are excluded.
- Concurrent participation in other therapeutic trials.
- Pregnant or nursing.
- Severe psychiatric illnesses (current schizophrenia, major depression with suicidal ideation).
- Use of PRN over the counter (OTC) pain medications (NSAIDs, etc.) on day of MRI scan.
- Use of PRN narcotic pain medication 48 hours prior to MRI scan.
- Active substance disorder in the past 24 months, as determined by subject self-report.
- Current, habitual, or previous use within the last 12 months of artificial nails, nail enhancements, or nail extensions that cover any portion of either thumbnail. Exceptions, including brief and/or occasional use, may be permissible at the discretion of the principal investigator.
- Contraindications to fcMRI, fMRI, or ¹H-MRS methods. (see above section)
- History vascular surgery in lower limbs or current lower limb vascular dysfunction.
- Any impairment, activity or situation that in the judgment of the Study Coordinator or Principal Investigator that would prevent satisfactory completion of the study protocol.

8.2. Study Enrollment Procedures

8.2.1. Recruitment

The primary recruitment method will be through phone solicitation of participants currently enrolled in the Chronic Pain and Fatigue Research Registry (University of Michigan Institutional Review Board # HUM00063489, PI: [name]). These individuals reside mainly in Southeast Michigan and have previously agreed to being solicited regarding participation in clinical trials.

We will also utilize the University of Michigan research recruitment portal www.UMClinicalStudies.org. This online portal has been created by the CTSA sponsored Michigan Institute of Clinical Research (MiCHR) to facilitate study team-volunteer communications. This website posts all available, ongoing research projects for interested volunteers and is available to the general community as well as the University of Michigan internal workforce and engages social networking to promote U-M research activities.

Other avenues that will be used to recruit patients include posting publically accessible flyers throughout University of Michigan clinics, public advertisements in the *AnnArbor.com*, the *Metro Times* and the *Detroit Free Press*, participation in the *Fibromyalgia Workshop* held at the UM CPFRC, and other local media outlets.

[figure not shown]
Participants will be recruited into the study by a dedicated member of the study team. All materials used for recruitment, and ongoing participant engagement, will be approved by the University of Michigan IRB. The initial step will be a telephone screen in which the inclusion and exclusion criteria will be described along with the general procedures for the study. Potential participants will have an opportunity to ask questions about the study involvement and if still interested will be invited to attend a screening visit.

At the screening visit, potential participants will go over the study requirements in more thoroughly with the study coordinator. They will sign the informed consent document at this time if they wish to proceed with the screening exam. Once screened, and deemed eligible for the study they will be considered “enrolled”.

All potential volunteers will be assigned a unique screening ID. Those volunteers who do not meet the eligibility criteria or who choose not to participate in the study at either the telephone Pre-Screen or the Screening Visit will be logged. Personal identifiers will be kept until the study has been closed to recruitment, at which time they will be destroyed. This will prevent repeat screenings of potential volunteers.

8.2.2. Informed Consent

The informed consent document will be approved by the University of Michigan IRBMED. The informed consent interview will be conducted by trained study staff and will include a verbal and written explanation of the study, including the purpose, testing procedures, time commitment, inclusion/ exclusion criteria, risks and benefits, alternative treatments, confidentiality, compensation, study personnel contacts, and required regulatory information. All individuals will be given the opportunity to ask questions. Once all questions and concerns are addressed to the participant’s satisfaction, the participant will sign the consent form. Only the subject herself will sign the consent form. Following informed consent, the study participant will be assigned a unique study identification number.

From this point forward, only the study ID number will be used to identify the individual, and the signed informed consent document will be stored securely and separately from all other research materials.

8.3 Screening and Enrollment

Potential subjects who are interested in participating in the study will be contacted by a member of the study team responsible for enrollment. Interested candidates will have the study and the eligibility criteria explained to them. If at this point they wish to continue with enrollment the candidate will be invited to participate in a study screening visit

The screening visit begins with the informed consent interview. Once the subject has formally consented to participate they will undergo a screening examination by a member of the study team. This includes:

- Completing demographic, sociodemographic, and medical history questionnaires
- Reviewing patient's self-reported 7-day recall VAS pain scale and Brief Pain Inventory (BPI)
- Assessing fibromyalgia status by tenderpoint examination and completing Fibromyalgia Symptom Questionnaire (FSQ) [*FM and HC cohorts*] and Fibromyalgia Impact Questionnaire (FIQ-R) [*FM cohort only*]
- Conducting a physical assessment (height and weight)
- Completing Psychological Screening questionnaires (HADS, PHQ-9)
- Administering a urine pregnancy test to women of childbearing potential
- Tenderpoint examination
- Reviewing current medications and therapies with subject.

The subject will be deemed enrolled upon meeting the study eligibility criteria. At the completion of screening visit, the subject will be provided with a copy of the informed consent document and a study schedule of appointments.

9. INVESTIGATIONAL PLAN

9.1. Acupuncture Treatments

9.1.1. Randomization and Blinding

After each FM participant has given written informed consent, they will be randomized to one of two arms: EA or ML. Computer generated random numbers will be used to develop the randomization scheme which will utilize a permuted block design, with variable size (4, 6, 8). This will help reduce the chance of participants breaking the blind and determining the next patient's assignment. Sealed envelopes will be generated by an individual in the Chronic Pain and Fatigue Research Center that will have no access to the study data nor influence on outcome assessment. Participant treatment allocation within these envelopes will be given to the acupuncturist on each participant's first treatment day. The acupuncturist will open the envelope to determine to which group the subject has been randomized. Following randomization, FM participants will receive 8 acupuncture treatments over the course of a month (two times per week for four weeks). During all treatment sessions, participants will be blind folded to ensure masking of the treatments. All acupuncture and sham treatments will be performed by a trained acupuncturist with board certification from the National Certification Commission for Acupuncture and Oriental Medicine.

The statistician and the study PIs will remain blinded until the study database is locked. The only study personnel that will not be blinded are the acupuncturists and the project manager, in order to facilitate randomization codes and treatment delivery. Due to this study utilizing dual database data entry, un-blinded non-essential personnel may need to enter data. However, this entry will not occur until the participant has exited trial (*see 12.2 Data Management*).

9.1.2. Electro-Acupuncture (EA)

This group will receive EA at 3 pairs of real acupoints: right side LI-11 to LI-4, left side GB34 to SP6, and bilateral ST36. Needles will also be inserted in Du-20, right ear shenmen, and left LV3. EA needles will be stimulated with low intensity, low frequency (2 Hz) electro-acupuncture using a constant-current electro-acupuncture device which allows for flexible setting of pulse width (1ms), frequency (2Hz), and shape (biphasic rectangular) parameters. The current intensity will be set at the midpoint between sensory and pain thresholds. Stimulation will last 25 minutes per session. **Selection of active needle sites:** Different types of acupuncture have been reviewed in detail [78]. These reviews emphasize the heterogeneity of traditions and styles even within a specific school of acupuncture. The optimal needle sites for FM have yet to be defined; consequently, the selection of active acupuncture sites is based on treating the predominant FM symptoms including: 1) diffuse, chronic myofascial and joint pain; 2) headache; 3) gastrointestinal pain and dysfunction; 4) disrupted or non-restorative sleep; and 5) chronic fatigue and weakness.

EA device: <http://www.harmonymedical.co.uk/product/3153-as-super-4-digital-needle-stimulator>

9.1.3. Mock Laser (ML)

For mock laser treatment, a laser acupuncture device (VitaLaser 650, Lhasa OMS) will be positioned 1-2cm over all of the same acupoints used in EA. There will be no palpation prior to positioning these devices, and there will be no physical contact between device and skin. The laser will not be turned on during the treatment. Switching the Timer toggle to 10 minutes for “on” and to 5 minutes for “off” will produce an audible click, as detailed by Irnich et al. [74, 75]. ML treatments will last 25 minutes per session.

ML device: http://www.lhasaoms.com/Vita_Laser-47-1300-page.html

9.1.4. Deception

One of the aims of our research is to study whether acupuncture alters the way the brain processes pain signals. To do this we needed to compare an active acupuncture treatment to an inactive, or “sham”, acupuncture treatment, however to maximize patient participation and retention throughout the course of the study, it is important that those receiving the sham treatment believe that they are in fact receiving active treatment. For this reason, the sham/inactive acupuncture treatment, ie. "mock laser", is to be described as non-traditional "laser acupuncture" in the informed consent document and throughout the IC process and study materials. It is described as a Placebo Comparator: Non-tradition Acupuncture" in Clinicaltrials.gov.

The sham treatment poses no additional risk to the subject. All participants regardless of assigned group will be debriefed by the Project Manager at the conclusion of their final visit (visit 12).

9.2. Pain Outcome Measures

Pain outcomes will be assessed at the University of Michigan by trained clinical research coordinators.

9.2.1. Clinical Pain

Pain severity and functional interference due to pain will be assessed using the Brief Pain Inventory (BPI). The BPI has been recommended by IMMPACT as a measure of choice for the assessment of pain in clinical research [79]. Clinical pain immediately before and after resting MRI scans will also be assessed using a 10cm visual analog scale, anchored by “no pain” and “worst pain imaginable.” Visual analog scales are used commonly by our group and others in the assessment of clinical pain.

9.2.2. Quantitative Sensory Testing

We will use the MR-compatible Multidimensional Automates Sensory Testing (MAST) System (US Patent No. 9,307,906)[80], which features a control computer running custom-design software, a touch screen display for patient feedback, and a wireless pressure actuator. The pressure actuator applies blunt force, delivered by a 1-cm² hard-rubber probe, to the thumbnail bed. The probe is attached to a cylindrical transducer housed inside a plastic “joystick” designed to be held comfortably in either hand. The transducer is driven by a miniature servo-motor

and a digital load-cell measures the exact pressure applied to the thumb to ensure accurate and repeatable testing.

Our group has extensive experience using thumbnail pressure as an evoked pain stimulus and its validity in the measurement of pain sensitivity has been discussed extensively [45, 81-88]. The MAST system will deliver an ascending series of 5-s duration stimuli at 25-s intervals, beginning at 0.25 kg/cm² and increasing in 0.25 – 0.50 kg/cm² intervals up to tolerance or to a maximum of 10 kg/cm² to the patient's dominant thumbnail. Pain intensity will be rated after each stimulus on a 0-100 numerical rating scale (NRS), with "0" representing "no pain" and "100" representing "extreme pain". These ratings will be used to compute pain threshold and a psychophysical function of each subject's suprathreshold pain sensitivity with pressure intensity and pain magnitude represented on the x- and y-axes, respectively. These curves will be used to compare single subject and group changes in pain sensitivity longitudinally throughout each project. These methods have been used extensively in our group to assess sensitivity to experimental stimuli.

Any data elements that are not obtained during the QST sessions due to unplanned yet common circumstances for this type of behavioral research (e.g., patient or facility time constraints, technical issues with equipment, or patient refusal to complete a particular test) will be considered "missing data" and will not be reported as a protocol deviation.

9.2.3. Cuff pain and Conditioned Pain Modulation.

Calibrated cuff pain stimuli will be delivered to the gastrocnemius area of the dominant leg using a validated cuff pain device that has been recently adapted to the MRI scanning environment. A computer controlled air compressor (Hokanson Rapid Cuff Inflator) will inflate the cuff to a pre-specified pressure, and maintain the pressure at that level. Subjects will participate in two separate test sessions of cuff pain on different days: one training session and one brain imaging session. In both sessions, pressure will be maintained for blocks of 14 seconds during the evoked pain fMRI scan to evaluate brain response to experimental pain. Pressure pain will also be applied for a continuous 6-minute period in a separate scan to evaluate functional brain connectivity response to deep pain (see below). One advantage to using cuff algometry pain is that unlike more superficial methods (e.g. heat pain), cuff pain responses are unaffected by sensitization or desensitization of the skin, indicating that this procedure primarily assesses sensitivity in muscle and other deep tissues. We have considerable experience applying these techniques in both healthy adults and chronic functional pain patients, and have found that all subjects are able to tolerate these procedures without any lasting discomfort. We will also repeat the thumbnail pain procedures above during and after the application of cuff pain to the gastrocnemius in order to assess conditioned pain modulation, which is used to evaluate the descending inhibitory pain modulation systems in the brain. During this test, alternating (on) and (off/touch) pressures will be applied to the thumbnail bed of the patient's dominant hand using a computer-controlled pneumatic pressure device compatible within the fMRI scanner environment. This system uses the QST Suite (Arbor Medical Innovations, Ypsilanti, MI, USA) Windows software to design the pneumatic pressure profile generated by the IPC-1000 pressure controller (Arbor Medical Innovations, Ypsilanti, MI, USA) via a USB link.

Training Session. A training session with the cuff will be used to familiarize subjects with the stimuli and rating procedures and determine appropriate stimulus intensities to be used subsequently in the imaging session (see below). This will take place during the in-clinic evaluation visit. During training, subjects will be maintained in a seated position in a chair with the left foot resting on a support at a slightly elevated position (but at a lower level than that of the hips, in order to facilitate blood circulation in the leg).

Testing will begin with an ascending series of pressure stimuli starting at 60 mmHg and increasing 20 mmHg increments. Ten seconds after the end of each stimulus, subjects will complete two 0-100 numerical rating scales: pain intensity (0 = "no pain", 100 = "worst pain imaginable/extreme pain") and pain unpleasantness (0 = "neutral", 100 = "extremely unpleasant"). The ascending series will end when a pain intensity rating of >70/100 is obtained. A descending series will then be administered starting with the last stimulus delivered during the ascending series and decreasing in 20 mmHg decrements until a pain intensity rating of 0/100 is obtained. For each pressure delivered, the mean pain rating obtained from the ascending and descending series will be calculated and then plotted against the corresponding pressure level to obtain a first "approximate" stimulus-response (S-R) curve. From this curve, the pressure values corresponding to pain intensity ratings of 10, 20, 30, 40, 50, 60 or 70/100 (i.e., "Pain10" to "Pain70") will be obtained by interpolation. In addition, the highest pressure value that was consistently rated as non-painful (i.e., associated with a pain intensity rating of 0 in both

ascending and descending series) will be defined as Pain0. As the awareness that the next stimulus will be higher (or lower) is likely to bias the ratings, a new S-R curve will then be calculated based on the ratings recorded during the presentation of these Pain0-Pain70 stimuli in pseudorandom order. Adjusted Pain0-Pain70 stimulus pressures will be determined by interpolation from this new curve. At the end of this calibration phase, subjects will receive each of the adjusted Pain0-Pain70 stimuli three times, for a total of 24 stimuli. The stimuli will be delivered in a pseudorandom order in three separate runs (8 stimuli per run).

Based on this testing, subjects will be eligible for participation in the imaging session if they are able to reliably differentiate stimuli of different intensities (i.e., if they reported increasing pain intensity ratings in response to stimuli of increasing intensity). This training session will have the effect of rendering subjects non-naïve to the experimental conditions in the imaging session, an aspect that might be argued to have some impact on the imaging results (particularly with regard to brain activity underlying cognitive and emotional functions). However, the training session has several advantages that outweigh these concerns: (1) identification and exclusion of individuals with unstable ratings, (2) a thorough training in the use of the rating scales, and (3) the reduced potential for developing experiment-related anxiety and head motion in the imaging session.

9.2.4. Visual Stimulation Assessment.

In addition to hypersensitivity to painful stimuli applied to the body, many chronic pain patients report hypersensitivity to nonpainful sensory stimuli, including to auditory, olfactory, and visual stimulation [81, 89, 90], suggesting a global state of multisensory amplification in centralized pain. To measure nonsomatic sensitivity, we will present to each participant a series of nonpainful yet aversive visual stimuli [91]. This 10 min task, conducted both inside and outside of the MRI scanner, consists of different visual stimuli presented in an alternating block design. The control stimulus is a fixed crosshair centered in the middle of a solid color background, whereas experimental stimulus is a flashing annulus checkerboard. These stimuli will be interleaved into independent 10-30 second blocks throughout the duration of the task. Participants will view the stimuli on either a standard LCD computer screen or through video goggles. Stimuli will be adjusted to varying degrees of frequency (checkerboard flashing only), color, shape, motion, and/or brightness level, and rated on a NRS and/or Box Scales[87] of sensory intensity and unpleasantness. No adverse events were associated with this task in a previous study of chronic pain patients (HUM00021096). However, to avoid possible adverse events in vulnerable patients, this visual stimulation task will not be performed if the participant has a history of migraines. These participants will still be allowed to complete all other QST procedures.

9.2.5 Assessment of Diet.

To assess typical dietary intake over the last 12 months we will use the 80out 2007 Harvard green FFQ questionnaire, which is a 61-item semi quantitative food frequency questionnaire that takes on average 20 minutes to complete. The semi-quantitative food frequency questionnaire have been developed at Harvard University is the result of over thirty years of continued development, evaluation, refinement and re-evaluation. It was originally created to be used as a self-administered, mailed questionnaire. The reproducibility and validity of the questionnaire has been assessed by comparing its estimates with those of diet records or multiple 24-hour recalls and with relevant biochemical indicators of nutrient intakes. Such studies have been conducted among adults of all ages and both sexes, and among a variety of socio-economic groups; many of these validation studies have been published [92-94]. The results of the validation studies have indicated that the method is remarkably robust; similarly valid results have been obtained from virtually all the groups that we have studied. We will give participants the FFQ once at baseline to take home and complete in the following week. FFQ will be returned via mail and all participants will receive \$10 for completion of the FFQ.

Imaging session. On the day of the imaging session, the Pain0-Pain70 pressures will be briefly recalibrated prior to scanning using procedures similar to those used during the training session. The first “approximate” S-R curve, however, will be calculated based on the ratings of Pain0, Pain10, Pain40 and Pain70 from the training session (instead of the full ascending and descending series). The Pain0-Pain70 stimuli pressures interpolated from this curve will then be presented in a pseudorandom order for calculation of an adjusted S-R curve. The definitive Pain0-Pain70 pressures used during fMRI will be determined by interpolation from this latter curve.

During the fMRI scan runs, subjects will receive three pressures: touch (30mmHg), equal pressure (130mmHg) and an equal pain condition (P40; 40/100). Each stimulus will be preceded by a 4-second visual cue (a cross changing color from black to green) that signals the upcoming stimulus to limit the stimulus-onset startle reflex. Ten seconds after stimulus offset, subjects will be presented with the intensity and unpleasantness scales, each for 10 seconds. Cuff pressure calibrated to each subject's Pain30-50 will also be applied for a continuous 6-min period in a separate fMRI scan to evaluate functional brain connectivity response to tonic deep pain. (see below)

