9.4.2. Baseline Behavioural Session – V1

- Review inclusion/exclusion criteria to assess patient's continued eligibility for enrolment
- Urine pregnancy test for women of childbearing potential
- Administer Neuroimaging Safety Screen
- Evaluate and record any changes in concomitant medications
- Collect:
 - BPI
 - FSQ
 - PROMIS-29
 - Perceptions of Bodily Sensations [PBS]
 - Pain Catastrophizing Scale [PCS]
 - PainDETECT
 - Fibromyalgia Impact Questionnaire [FIQ-R] (*FM cohort only*)
 - Desire of Relief Scale [DRS] (*FM cohort only*)
 - Expected Relief Scale [ERS] (*FM cohort only*)
 - Multiple Ability Self Report Questionnaire [MASQ]
 - Pittsburgh Sleep Quality Index [PSQI]
 - VAS -Present Pain
 - Menstrual Questionnaire
 - After-Cuff Questionnaire (*post QST assessments*)
 - *Harvard Food Diary (FFQ)*
- Quantitative Sensory Testing (QST) – Assessment of ascending pressure pain thresholds and conditioned pain modulation (CPM) using MAST and cuff, and visual stimulation assessment.
- Collect and record pre-treatment adverse events
- Patients will be reminded to refrain from taking any OTC pain medication on the day of the scan (NSAIDs, etc.)
- Patients will be reminded to refrain from taking any PRN narcotic pain medication 48 hours prior to the MRI scan.

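### Minor safety improvement: the flashing-checkerboard task is skipped only for migraine, and no printed control criterion names seizure disorder

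*Combined protocol and SAP*

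**What the plan says.** Section 9.2.4 describes a 10-minute task, run both inside and outside the scanner, in which a flashing annulus checkerboard alternates with a fixed crosshair. Flash frequency and brightness are varied, and no limit is given for either. The section reports that "No adverse events were associated with this task in a previous study of chronic pain patients". As a precaution for vulnerable patients it then adds a single skip rule: "this visual stimulation task will not be performed if the participant has a history of migraines". Skipping costs nothing else: "These participants will still be allowed to complete all other QST procedures".

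In section 8.1.2, the FM exclusion list includes contraindications to the electrostimulator, among them "cardiac rhythmic disorders, seizure disorders, any skin disorders in the vicinity of the electrode". The control list has no counterpart. It does exclude for contraindications to the imaging methods, by reference back to the FM item, and for any impairment or situation "that would prevent satisfactory completion of the study protocol", in the judgement of the coordinator or investigator.

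Section 8.3 collects relevant history at the screening visit: "Completing demographic, sociodemographic, and medical history questionnaires" and "Reviewing current medications and therapies with subject". Section 9.4.2 lists "Administer Neuroimaging Safety Screen" at V1. The control schedule in section 3.2 marks visual stimulation at V1, includes it in the V2 imaging session, and carries a familiarization-only footnote at V0 on the row that combines pain assessment and visual stimulation.

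**The concern.** The protocol has already decided to guard this task with a named history. For a flashing stimulus of varying frequency and brightness, a seizure disorder is an obvious second history to name, and it is not named. FM patients are covered, but only because a different device, the electrostimulator, carries that contraindication. Controls receive no electrostimulation, so the exclusion does not reach them, although they see the same stimulus.

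What is at stake is the safety of a rare control participant. Followed literally, the printed rule would let a control with a known seizure disorder do the task unless staff discretion or a document outside this file intervened.

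**Working it through.** No calculation applies, so the check sets the relevant sections side by side.

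1. **Stated skip conditions (9.2.4).** There is one, a history of migraines.

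2. **FM patients (8.1.2).** Seizure disorders are an exclusion at enrolment through the electrostimulator item. A seizure skip rule in 9.2.4 would therefore change nothing for them.

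3. **Controls (8.1.1 and 8.1.2).** Inclusion criteria: 6. Exclusion criteria: 16. Total 6 + 16 = 22, of which 0 name seizure disorder. The nearest items are:
   - head injury with substantial loss of consciousness, which is a different history;
   - imaging contraindications, which point to the FM item. The examples there are metal and surgical items, but that list is expressly not exhaustive and refers to a fuller description in the DSM Plan (Appendix A, not supplied);
   - the judgement clause, which asks whether the participant can complete the protocol, not whether a particular stimulus is safe for her.

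4. **Exposure of controls (3.2).** Up to 40 controls are scheduled for the task at V1 and V2. The V0 footnote sits on a combined row, and the screening list in 9.4.1 does not mention familiarization, so the text does not settle whether the flashing stimulus is shown at V0. For that reason no total number of exposures is given here.

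5. **Steps that could catch a seizure history in a control.**
   - The medical history and medication review at V0 collect the information, but no printed rule links a seizure history to omitting the task.
   - The eligibility reviews at V1 and V2 reapply the same list, so they add no criterion.
   - The Neuroimaging Safety Screen comes at V1, ahead of the V1 task in the order listed, but after any V0 familiarization. Its content is not supplied.

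6. **Effect on the analysis (section 11).** The visual task appears in none of the Aim 1 to 3 hypotheses, power calculations or stated analyses.

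**The case against.** The best reply is that the gap may not exist in practice. The imaging-contraindication criterion leads to an open-ended list and to a DSM Plan that cannot be seen here. The pre-screen interview, medical history form, eligibility checklist and imaging forms listed in section 17 are also unseen. Any of them may ask about seizures. Trained staff take a medical history before testing, and the investigator may exclude at discretion. Prior use of the task produced no adverse events. Much of this stands: the finding is limited to the printed text, and these layers may well catch the rare case. Two parts carry less weight. The earlier experience was in chronic pain patients, not healthy controls, and the sponsor added the migraine rule in spite of it. A discretionary clause about completing the protocol is also a weaker safeguard than a named condition.

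A reader might infer that controls with epilepsy will be enrolled and shown the stimulus with nothing in the way. The documents do not support that, for the reasons just given. A reader might also infer that FM patients share the gap. For seizure disorders they do not, since they are excluded at enrolment.

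Finally, a reader might want photosensitivity added as a general skip condition. That would be a mistake unless it is defined. Section 9.2.4 explains that many chronic pain patients are hypersensitive to visual stimulation and that the task exists to measure such sensitivity. A loosely worded criterion could remove those FM patients and distort an FM-control comparison on this task.

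**Conclusion.** The point holds as a minor, low-cost safety improvement. Migraine is the only printed skip condition, and 0 of 22 printed control criteria name seizure disorder, although up to 40 controls are scheduled for the task. The count describes wording; it does not measure risk. The documents give no seizure prevalence, flash rate or brightness, so neither the number of controls affected nor the size of the hazard can be estimated.

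The conclusion assumes that the DSM Plan and the screening forms do not already contain the rule. If they do, all that remains is a missing cross-reference. There is no consequence for power, for the aims or for any stated analysis.

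**What to change.** In section 9.2.4, extend the skip condition to: *a history of migraines, or a history of seizure disorder (including photosensitive epilepsy)*. State that this is checked against the V0 medical history before any visual stimulation, including any familiarization at V0. Participants who skip still complete the other sensory tests, as the section already provides. If the DSM Plan or a screening form already covers seizure, a cross-reference in 9.2.4 is sufficient. Do not add an undefined photosensitivity criterion.

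The cost is one phrase, using history already collected. The downside is that a rare control loses one task that serves no stated hypothesis or analysis.
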